### 4.2. Inclusion criteria

Patients must meet all the following criteria in order to be included in the study:

1. Histological or cytological documented evidence of HPV16 positive (pre)malignant lesion following standard treatment
2. Patients with a tumor should have no evidence of residual disease based on physical examination at the completion of curative intent therapy
3. At least four weeks and less than sixteen weeks after last anti-tumor treatment
4. Willing and able to comply with the protocol and to provide informed consent in accordance with institutional and regulatory guidelines
5. Patients must be 18 years or older

NL48274.000.14

Phase I Study: Hespecta vaccination in HPV+ lesions

6. Patients of child-bearing potential should test negative using a serum pregnancy test and agree to utilize effective contraception during the entire treatment and follow-up period of the study (up to 2 months after the last vaccination)
7. Patients must be in good general health and ambulatory, with an ECOG performance status of 0 or 1 (appendix 1)

#### 4.3. Exclusion criteria

Patients who meet the following exclusion criteria will not be eligible for admission to the study:

1. Radiotherapy, chemotherapy or other potentially immunosuppressive therapy administered within 4 weeks prior to the enrolment visit
2. History of an autoimmune disease or other systemic intercurrent disease that might affect the immunocompetence of the patient, or patients receiving immunosuppressive therapy, except for topical application
3. History of a second malignancy except curatively treated low-stage tumors with a histology that can be differentiated from the current tumor or premalignant lesion
4. Receipt of another investigational product within the previous 4 weeks or at any time during the study period
5. Receipt of prior HPV directed immunotherapy
6. Hematology and biochemistry:
  - Absolute Neutrophil Count (ANC)  $< 1.5 \times 10^9/L$ , or platelet count  $< 100 \times 10^9/L$  or hemoglobin  $< 6 \text{ mmol/L}$ .
  - Serum (total) bilirubin  $> 2 \times$  upper normal limit (ULN);
  - Aspartate Aminotransferase (ASAT) or Alanine Aminotransferase (ALAT)  $> 2.5 \times$  ULN;
  - Alkaline phosphatase levels  $> 2.5 \times$  ULN;
  - Serum creatinine  $> \text{ULN}$  or calculated clearance  $\leq 40 \text{ mL/min/1.73 m}^2$  for patients with serum creatinine levels above the institutional normal value
7. Human immunodeficiency virus (HIV), chronic hepatitis B or C infection.
8. Any condition that in the opinion of the investigator could interfere with the conduct of the study

#### **4.4. Sample size calculation**

According to the clinical development paradigm for cancer vaccines as set by the Cancer Vaccine Clinical Trial Working Group (CVCTWG) [52] the current trial satisfies the criteria for being a proof-of-principle trial. The dose and schedule are investigated in proof of- principle trials, however, a definitive answer on the optimal setting for further trials should not be expected from a first-in-human study. For cancer vaccines, there may not be any linear association between dose, immunogenicity and clinical end points, therefore, the vaccine acute safety profile is not dose dependent. It is expected that the vaccine produces the desired biological effect across a broad-dose range. Primary end point used in this study is to determine biological activity i.e. T-cell immune response to the vaccine. Four different assays are used to evaluate the immunogenicity of Hespecta. These established complementary assays are conducted with blood samples taken at 4 time points (baseline and 3 follow-up time points after vaccine administration) , and are fully described in standard operating procedures (SOPs), including predefined criteria for positive and vaccine-induced response, and have been used and validated in a number of vaccine trials as published by our laboratory [17,32,33]. An immune response is identified if it was seen in at least 2 assays at 2 consecutive follow-up time points after the baseline assessment, in line with CVCTWG criteria. For proof-of-principle trials CVCTWG suggests a cohort size of at least 6 patients per dose [52]. As the CVCTWG already stated, the body of literature for optimizing the size of conventional phase 1 trials has little applicability to designing a proof-of-principle cohort trial because of the differences in the types of outcome measures and objectives. Here a cohort size of 6 patients per dose is used to determine safety and immunogenicity of Hespecta.

NL48274.000.14

Phase I Study: Hespsecta vaccination in HPV+ lesions

## 5. TREATMENT OF SUBJECTS

### 5.1. Investigational product/treatment

The vaccine consists of the Amplivant® TLR-ligand conjugated to 1) the HPV16 E6 71-95 peptide and 2) the HPV16 E6 127-158 peptide, each harboring multiple potential Th and CTL epitopes (see paragraph 1.6). The design of these long peptides was based on high immunogenicity in patients vaccinated with the HPV16-SLP and healthy donor who spontaneously responded to these peptides. Amplivant® was chosen for bioactivity (see paragraph 1.5) on human DCs and feasibility concerning GMP production (see IMPD)

### 5.2. Use of co-intervention (if applicable)

The effect of the vaccine could be modified by immunosuppressive therapy, which is therefore an exclusion criterion (see section 4.3). Other therapeutic options like surgery or chemotherapeutic treatment should be avoided. Patients must agree to utilize effective contraception (female of child-bearing potential only) during the entire treatment period of the study and during follow-up.

### 5.3. Escape medication (if applicable)

No specific antidotes for the Hespsecta vaccine are available. Appropriate drugs and medical equipment to treat acute anaphylactic reactions should be available, and study personnel will be trained to recognise and treat anaphylaxis. Supportive measures will be used as indicated in case of AEs. When side-effects from the vaccination occur it is allowed to use paracetamol for pain relief of the local injection site, or anti-histamines when an allergic reaction occurs at the site of vaccination to alleviate the complaints.

NL48274.000.14

Phase I Study: Hespsecta vaccination in HPV+ lesions

## 6. INVESTIGATIONAL PRODUCT

### 6.1. Name and description of investigational product(s)

Hespsecta, consisting of two HPV16 E6 synthetic peptides (E6 71-95 and E6 127-158) conjugated to the Amplivant® TLR-ligand, is produced in the Interdivisional GMP-Facility LUMC (IGFL) of the LUMC Department of Clinical Pharmacy and Toxicology. Technical details regarding the Investigational Medicinal Product (IMP) or the production process are listed in the IMP Dossier (IMPD) that accompanies this protocol. Immunological and preclinical data concerning the IMP are described in the Investigator's Brochure (IB) accompanying this protocol.

### 6.2. Description and justification of route of administration and dosage

Two HPV16 E6 peptides conjugated to Amplivant® will be reconstituted in DMSO / Water For Injections (WFI) 20/80 v/v in a total volume of 0.10 mL. The peptides are dissolved in this volume at a dose of 1 µg per peptide (first group), of 5 µg per peptide (second group), 20 µg per peptide (third group) or 50 µg per peptide (fourth group). The dose needed to establish a strong T-cell response in HPV16+ cancer patients by i.d. injection is unknown. A dose escalation of 1, 5, 20 or 50 µg per Amplivant® conjugated peptide (respectively 100 times to 10 times lower doses than unconjugated SLP) was chosen.

The dose range is based on a 10-100 fold higher bioactivity of Amplivant® conjugated peptides in preclinical studies [40]. The starting dose of this dose escalation trial is based on preclinical murine experiments showing that a dose of 1 µg per Amplivant conjugated peptides resulted in no severe toxicity and a suboptimal immune response in that the magnitude of the immune response increased when mice were given a higher dose of vaccine. We reason that this provides the best scientific basis for the first dose to start with. Fifty µg of unconjugated peptides dissolved in Montanide ISA51 and injected s.c. induced a strong T-cell response in CxCa patients as well as in CIN patients [33,51]. As Amplivant® conjugated peptides are expected to induce T-cell responses more effectively compared to unconjugated peptides, the lowest dose known (50 µg per peptide) of unconjugated peptides able to induce T-cell responses is used as highest dose in this trial. From the starting dose of 1 µg per peptide an ascending dose range is proposed, evaluating four doses (1, 5, 20, 50 micrograms per peptide). Notably, the higher the dose the smaller the dose-fold increase between the doses (5, 4, 2.5 times), this should allow for maximal safety. Vaccination will be carried out three times with three weeks intervals, at least one month after the last conventional treatment. The vaccine will be injected i.d. at alternating sites of the thigh or the upper arm. The number of vaccinations and spacing of vaccine doses with intervals of three weeks is based on our previous immunotherapy trials with HPV16-SLP. We have chosen to inject i.d. because the vaccine targets to a dense network of cutaneous DCs. This i.d. injection instead of s.c. vaccination is warranted to get rid of the oil-depot with Montanide adjuvant used for s.c. injection, as this can occasionally be associated with late (1 year) severe vaccine site reactions [42]. GMP produced clinical grade Amplivant®-conjugated HPV16E6-SLP were used to pre-

NL48274.000.14

Phase I Study: Hespecta vaccination in HPV+ lesions

---

clinically test the potential toxicity of this new generation vaccine in animals. No mortality occurred and no adverse systemic effects were observed at 5 or 60 µg and was very well tolerated in New Zealand White rabbits, as described in detail in de IB.

### **6.3. Preparation and labeling of Investigational Medicinal Product**

Just before administration, the vaccine is reconstituted, prepared with excipients, and labelled for each individual subject, according to standard procedures at the Department of Clinical Pharmacy and Toxicology of the LUMC. The reconstituted and ready-to-administer vaccine contains both HPV-Amplivant® peptides dissolved in dimethylsulfoxide/water for injection 20/80 v/v. One dose for i.d. administration contains 1, 5 20 or 50 µg of each peptide in a total volume of 0.10 mL.

### **6.4. Drug accountability**

Drug accountability will be recorded by the responsible staff members of the Department of Clinical Pharmacy and Toxicology of the LUMC according to standard procedures.

NL48274.000.14

Phase I Study: Hespsecta vaccination in HPV+ lesions

## 7. METHODS

### 7.1. Main study parameter/endpoint

Primary objective is to determine the biological activity of Hespsecta that is able to induce HPV16 E6-specific T-cell immunity within a proposed dose escalation of 1, 5, 20 or 50 µg/peptide - conjugate in patients with HPV16+ tumors or premalignant lesions. Blood samples will be drawn and used in an array of complementary immunological assays (HPV16-specific proliferation assay, IFN $\gamma$ -ELISPOT, cytokine bead array and multiparameter flow cytometry analysis) to assess the biological activity of Hespsecta. These established assays are performed at 4 different time points (baseline and 3 time points after start of vaccination). Vaccine induced immunity in the different assays is defined if the response after vaccination is at least 3-fold higher than the pre-vaccination response. Biological activity is identified if it was seen in at least 2 assays at 2 consecutive follow-up time points after the baseline assessment, in line with CVCTWG criteria.

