#### 7.9.5. Immunological assessments

##### 7.9.5.1. HPV16 E6 and E7 peptide-specific proliferation assay

HPV16 E6 and E7 peptide-specific proliferation is determined using a short-term (6-day) assay. This assay has been published and found to be related to clinical outcome [10,18,32,53,54]. The average and standard deviation of the 8 medium only control wells are calculated and the cut-off is defined as this average plus 3xSD. The stimulation index (SI) is calculated as the average of 8 experimental wells divided by the average of the 8 medium control wells. A positive proliferative response is predefined as a SI of at least 3 and the counts of at least 6 out of the 8-wells must be equal or above the cut-off value [7].

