##### 7.9.5.2. HPV16 E6 and E7 peptide-specific cytokine bead array

Supernatants from the peptide-specific proliferation assay are used to perform a cytokine bead array and measure cytokine production (IFN $\gamma$ , TNF $\alpha$ , IL-4, IL-5, IL-10, and IL-2). Positive antigen-specific cytokine production (in pg/ml) is defined as a cytokine concentration above the detection limit and >2x the concentration of the medium control. A vaccine-induced response is defined as a value (SI or cytokine level) which is at least 3-fold higher than the pre-vaccination response [7].

NL48274.000.14

Phase I Study: Hespecta vaccination in HPV+ lesions

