#### 7.9.5.3. HPV16 E6 and E7 peptide-specific IFN $\gamma$ -ELISPOT for CD4+ T-cells

The 4-day IFN $\gamma$ -ELISPOT for the detection of HPV16 E6 and E7 peptide-specific CD4+ T cells is our standard and validated assay. Spots are counted with a fully automated computer-assisted-video-imaging analysis system (BioSys 5000). Specific spots are calculated by subtracting the mean number of spots in quadruplicate wells + 2xSD of the medium only control from the mean number of spots in experimental wells. Antigen-specific T-cell frequencies are considered to be increased compared to non-responders when specific T-cell frequencies are  $\geq 1/10,000$ . T-cell frequencies are considered to be boosted by the vaccine when they were at least 3-fold higher than those prior to vaccination [10,55,56,57].

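### The per-assay responder rule asks only for a 3-fold rise over baseline: it is not tied to the assay's positivity limit and has no rule for baselines at or below zero

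*Protocol*

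**What the plan says.** **The 3-fold rule.** Section 7.1 defines the assay-level response as: "Vaccine induced immunity in the different assays is defined if the response after vaccination is at least 3-fold higher than the pre-vaccination response". The Synopsis says the same. Section 7.9.5.2 repeats it for proliferation and cytokines: "A vaccine-induced response is defined as a value (SI or cytokine level) which is at least 3-fold higher than the pre-vaccination response". Sections 7.9.5.3 (ELISPOT) and 7.9.5.4 (flow cytometry) likewise define a boosted or vaccine-induced response by the 3-fold increase alone.

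**The positivity limits.** These stand in separate sentences:
- Proliferation (7.9.5.1): "A positive proliferative response is predefined as a SI of at least 3 and the counts of at least 6 out of the 8-wells" must reach the cut-off, which is the medium mean plus 3 SD.
- Cytokine bead array (7.9.5.2): positivity "is defined as a cytokine concentration above the detection limit and >2x the concentration of the medium control".
- ELISPOT (7.9.5.3): "Antigen-specific T-cell frequencies are considered to be increased compared to non-responders when specific T-cell frequencies are" at least 1/10,000.
- Flow cytometry (7.9.5.4): twice the medium control.

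**The ELISPOT value.** Section 7.9.5.3 corrects for background as follows: "Specific spots are calculated by subtracting the mean number of spots in quadruplicate wells + 2xSD of the medium only control" from the mean of the experimental wells. No lower bound is given.

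**The patient-level rule.** Section 7.1 continues: "Biological activity is identified if it was seen in at least 2 assays at 2 consecutive follow-up time points after the baseline assessment". Section 4.4 adds that the assay SOPs, which are not at hand, hold criteria for both a positive and a vaccine-induced response.

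**The concern.** A ratio to baseline is informative only when the baseline is clearly above zero. The protocol expects the opposite: the Synopsis and section 1.2 describe spontaneous HPV-specific responses in these patients as weak. Where the baseline is near zero, a small absolute change makes a large ratio. Where it is zero or negative, the ratio has no meaning.

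The positivity limits in 7.9.5 would screen out most such cases, but the text never makes them a condition of a vaccine-induced response. A sample can therefore be negative by the protocol's own limit and still count towards the primary endpoint. With 6 patients per dose, one misclassified patient moves a cohort's responder proportion by 1/6, about 17 percentage points.

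**Working it through.** **Step 1. Set the two definitions side by side.** The limits allow simple counter-examples:
- ELISPOT rising from 0.1 to 0.3 per 10,000: 0.3/0.1 = 3, so it is vaccine-induced. But 0.3 < 1 per 10,000, so it is not positive.
- SI rising from 0.5 to 1.5: 1.5/0.5 = 3, so it is vaccine-induced. But 1.5 < 3, so it is not positive. This case is less natural. Without a response SI centres near 1, and a rise from 1 to 3 already reaches the positivity limit.

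**Step 2. Why ELISPOT baselines fall to zero or below.** Specific spots = experimental mean − (medium mean + 2 SD). Assume Poisson wells with background 5 and a true response of 5 spots per well. Then SD ≈ √5 = 2.24, and the expected value is roughly 10 − (5 + 4.47) = 0.53. A real but weak response thus sits almost at zero after correction. With no response the centre is about 5 − 9.47 = −4.47.

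**Step 3. ELISPOT false rate.** The inputs are quadruplicate wells (7.9.5.3) and immunology samples at weeks 0, 6, 9 and 26 (7.9.3). Assumptions not in the document are Poisson counts, no true change over time, and independent samples apart from the shared baseline. A response means follow-up > 0 and ≥ 3 × baseline at weeks 6 and 9 or at weeks 9 and 26 (200,000 draws).

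| True state | Baseline ≤ 0 | Rule met at two consecutive visits |
|---|---|---|
| Background 5, stable response 5 spots/well | 36% | about 25% |
| Background 2–10, stable response 2–8 | – | 3–25% |
| No response, background 2–20 | 95–96% | 0.3–0.5% |

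The condition that the follow-up exceed zero was supplied here; the protocol does not state it. Without it, with no true response, two consecutive visits are flagged in about 8% (dividing one negative value by another) or 81–84% (checking only that follow-up ≥ 3 × a negative baseline). No laboratory would intend those readings, but the text does not exclude them.

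**Step 4. How much two consecutive visits protect.** In the 5/5 case the single-visit rate is 30.6%. If the visits were independent, the two-visit rate would be 2p² − p³ = 2(0.306)² − (0.306)³ = 0.187 − 0.029 = 0.159. The simulated rate is about 25%. The shared baseline explains the gap, since one low baseline can satisfy both visits.

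**Step 5. How much two assays protect.** The cytokine array uses supernatants from the proliferation cultures (7.9.5.2), so those two are not independent. The schedule of events (7.3.2, footnote 5) limits ex vivo staining to baseline and the early follow-up visit. If that means one visit, flow cannot supply two consecutive time points.

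**Step 6. The other assays.** Only ELISPOT has a stated subtraction that gives negative values. Proliferation with no response (assumed lognormal wells, one visit) meets the 3-fold rule in 0% at CV 0.3, 0.4% at 0.6, 5% at 1.0 and 12% at 1.5, so it matters only if wells are very variable. Cytokine and flow values near zero are exposed to the same ratio problem; no rate was computed for them.

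**Step 7. Effect of adding the positivity criterion.** The protocol does not give cells per well, so the 1/10,000 limit is taken as 5 or 10 specific spots (10 at an assumed 100,000 cells per well). For a stable weak response, the two-visit ELISPOT rate becomes 0–6% at a limit of 5 spots and below 0.1% at 10. With no response it is essentially zero. For proliferation the single-visit rate falls to at most 0.06%.

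**The case against.** Several stronger readings are tempting, and the documents do not support them.

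- **That the responder rule is only a 3-fold rise.** It is not. The 3-fold rise is the per-assay component, and biological activity also needs at least 2 assays at 2 consecutive follow-ups.
- **That up to 25% of patients would be false responders.** The 25% is for ELISPOT alone, at the worst point of the grid. If a second assay erred at the same rate and independently, the joint rate there would be 0.25² ≈ 6%, and at the low end 0.03² ≈ 0.1%. Independence is optimistic for the reasons in steps 4 and 5, so this shows direction only.
- **That pure noise drives the problem.** With no response the two-visit ELISPOT rate is only 0.3–0.5% once the follow-up must exceed zero, because the follow-ups are mostly negative too. The larger rates need a real, constant response close to the 2 SD correction.
- **That the protocol lacks positivity criteria.** All four assays have one. The defect is that they are not linked to the 3-fold rule.
- **That trial decisions rest on the count.** Section 9.1 plans descriptive statistics with 95% confidence intervals and states no responder threshold. The IDMC charter (14.2.2) bases escalation on safety data only.

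The SOPs cited in 4.4 may join the two definitions and may handle negative values. That point has weight, but it does not correct the definition the protocol prints for its primary endpoint. If the SOPs do link them, the protocol text is incomplete and should be brought into line.

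**Conclusion.** The point holds as a gap in the endpoint definition. The vaccine-induced rule in the Synopsis, 7.1 and 7.9.5.2–7.9.5.4 is not conditional on a positive follow-up sample, and nothing says how to treat a baseline that is zero, negative or below detection. ELISPOT is the assay mainly affected, cytokine and flow values less so, and SI little.

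The size can be given only for ELISPOT on its own: about 3–25% at two consecutive visits for a stable weak response, and 0.3–0.5% with none. These figures rest on assumed Poisson counts, the assumed background levels and an added requirement that the follow-up exceed zero. The patient-level false-responder rate is lowered by the 2-assay, 2-visit rule to an extent that the document does not allow one to compute. As no decision rule uses the responder count, this is a should-fix.

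**What to change.** In the Synopsis, 7.1 and 7.9.5, count a vaccine-induced response in an assay only if both conditions hold:

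1. The follow-up sample meets that assay's stated positivity criterion: SI at least 3 with 6 of 8 wells at or above the cut-off; above the detection limit and more than twice medium; at least 1/10,000; or twice medium.
2. The value is at least 3 times baseline, where a zero, negative or below-detection baseline is first set to a prespecified positive floor, such as the assay's detection limit.

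The floor should not be derived as one third of the positivity limit. For flow that gives 2/3 ≈ 0.67 of the medium control, which lies below background. For ELISPOT, three times such a floor is just the positivity limit again, so for floored baselines condition 2 would add nothing. The SOP wording should be checked against the revised text.

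The change needs no extra samples, patients or assays. Its cost is a somewhat lower reported responder rate, because rises that stay below the positivity limit no longer count.

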### 7.2. Secondary study parameters/endpoints

Safety will be determined by the incidence rate at each dose level based on the following safety parameters: adverse events (AE) and serious (SAE), changes in hematology and chemistry values, including those associated with hepatic and renal function, and assessment of physical examinations, vital signs and performance status using NCI-CTCAE version 4.0

[figure not shown]
([http://ctep.cancer.gov/protocolDevelopment/electronic\\_applications/ctc.htm#ctc\\_40](http://ctep.cancer.gov/protocolDevelopment/electronic_applications/ctc.htm#ctc_40)).

NL48274.000.14

Phase I Study: Hespsecta vaccination in HPV+ lesions

